## 2) Objectives

The overall objective of this study is to test the efficacy of virtual family-centered rounds (FCR) compared to standard rounds for NICU patients and to conduct an intervention evaluation of the virtual FCR intervention.

**Aim 1: Evaluate the impact of virtual FCR on parental activation and wellbeing.** The primary outcome will be FCR parent attendance proportion (number of round encounters with a parent present – either virtually or in person – divided by total number of round encounters). Increased parent FCR attendance would increase the delivery of best practice. We will also compare parent experience (Child HCAHPS) and parent activation (P-PAM) at discharge and parent distress and quality of life at 0, 30, 60, and 90 days from discharge between assigned trial arms. Parent wellbeing promotes neonatal wellbeing.

- *Hypothesis1a: The virtual FCR (intervention) group will have a higher parent FCR attendance proportion compared to the standard FCR (control) group.*
- *Hypotheses1b: Parents of virtual FCR neonates will report (a) better experience, (b) higher activation, (c) less distress, and (d) better quality of life compared to parents of standard-of-care neonates.*

**Aim 2: Evaluate the impact of virtual FCR on neonatal outcomes.** We will compare breast milk feeding at discharge and 90 days from discharge, growth failure, medical errors, and NICU length of stay between assigned trial arms.

- *Hypotheses2: Virtual FCR neonates will have (a) greater breast milk feeding, (b) reduced growth failure, (c) fewer errors, and (d) shortened length of stay compared to standard-of-care neonates.*

**Aim 3: Conduct a mixed methods evaluation of the virtual FCR intervention.** We will measure all five RE-AIM dimensions using quantitative (chart review, surveys) and qualitative (observations, interviews) methods. Observations will be of NICU FCR; interviews will be with intervention arm parents and NICU providers. We will use a convergent design and merge data in the analysis and reporting phases.

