**5) Study Timelines**

We anticipate this trial will begin ~2/1/2023. We will begin enrolling subjects at trial onset. We will enroll subjects (neonates) and assign to either the intervention or control arm for 12 months. Each subject (neonate) will be included for the duration of their hospitalization.

We will follow this 12-month period with 1 month of rounding observations for data collection. We will also continue to collect surveys at 0, 30, 60, and 90 days from discharge. Therefore, survey data collection will continue until 16 months from the trial onset.

Regarding qualitative interviews for the intervention evaluation (Aim 3), those will continue for 18 months from the trial onset.

The estimated date to complete this study is therefore ~8/1/2024.

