**DATA COLLECTION:** Data collection will include daily weekday virtual FCR observations; parent surveys; and review of the EHR, incident reports, and helpdesk technical issues log. Outcomes (for Aims 1-3) will include the following: FCR parent attendance proportion (captured using weekday rounding observations), length of stay (captured using EHR data), breast milk feeding initiation and breast milk feeding at discharge (captured using EHR data) and at 90 days after discharge (captures via parent via parent/guardian survey), growth failure and growth velocity (captured using EHR data), time to first social work contact (captured using EHR data), temperature instability (captured from an existy NICU quality dataset), feeding difficulty (captured from an existy NICU quality dataset), central line-associated bloodstream infection (captured from an existy NICU quality dataset), central line days (captured from an existy NICU quality dataset), antibiotics days (captured from an existy NICU quality dataset), medical errors (captured using data from EHR, incident reporting system, and solicited reports), 30-day revisit and readmission (captured via EHR and survey) parent experience and family-centered care (captured via parent/guardian survey at discharge), parent activation (captured via parent/guardian survey at discharge), parent distress: depression and anxiety (captured via parent/guardian survey at 0, 30, 60, 90 days from discharge), parent sleep (captured via parent/guardian survey at 0, 30, 60, 90 days from discharge), and parent quality of life (captured via parent/guardian survey at 0, 30, 60, 90 days from discharge).

RE-AIM (Aim 3) implementation evaluation data collection will include the

**PROTOCOL TITLE: Virtual Family-Centered Rounds in the Neonatal Intensive Care Unit:  
A Randomized Clinical Trial**

following: subscribed vs. not subscribed parents among intervention-arm parents, heterogeneity of intervention effects (interactions between neonate/parent characteristics and the intervention effect), virtual FCR attempts with technical issues (sounds, video, other), trial-related 24/7 helpdesk line calls, ExtendedCare wait time when parent(s) join, ExtendedCare connection time, device model (e.g., iPhone, Android, etc.) that parent uses to connect to the ExtendedCare visit, interruptions requiring a break in rounds due to a delivery or new admission, and virtual FCR use with NICU parents post-trial (maintenance).

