### **Methods for additional analyses (e.g. subgroup analyses)**

We will conduct mediation analysis to evaluate relationships between parent activation and the other secondary and exploratory outcomes. We will also evaluate relationships between FCR attendance and the other outcomes. For example, the intervention effect on HRQOL may be mediated by FCR attendance with a dose-response relationship. Thus, if we find a positive intervention effect on HRQOL, we will explore FCR attendance mediation using similar methods. We anticipate that the intervention effect on the following outcomes will be mediated by FCR attendance with a dose-response relationship: parent experience, family-centered care, parent activation, parent HRQOL, length of stay, and breastmilk feeding.

We will explore heterogeneity of the treatment effects, using rigorous analyses based on including interaction terms for the candidate effect modifier and the intervention effect term(s).

Candidate effect modifiers will include residence-to-NICU distance, neighborhood health conditions, parent race and ethnicity, parent transportation security, other children dependents, parent computer/smart device access, parent internet access, and parent digital literacy score. For these terms, each will be evaluated without correction for multiple discovery. Other candidate effect modifiers will be evaluated as part of a comprehensive examination of intervention effects and for these, we will control the false discovery rate at 10%.

We will decompose the FCR parent attendance outcome measure by the type of attendance to separate the in-person and virtual components. We will explore the type of attendance as an outcome variable and as a predictor of the secondary outcomes. We will include a statistical exploration within the intervention arm for whether higher virtual FCR attendance is associated with differences in in-person FCR attendance. Additionally, we will fit regression models for each secondary outcome that simultaneously include measures of both virtual and in-person FCR attendance, allowing us to assess and compare whether the incremental benefits of higher FCR attendance are similar between both types of attendance.

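### Whole-stay attendance is planned as mediator and predictor of length of stay, so any drift in attendance over the stay biases that exploratory analysis, in either direction

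*Combined protocol and SAP*

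**What the plan says.** The protocol (Objectives, Aim 1) defines attendance as the "number of round encounters with a parent present – either virtually or in person – divided by total number of round encounters". Study Timelines adds: "Each subject (neonate) will be included for the duration of their hospitalization". Procedures Involved says how it is observed: "FCR parent attendance proportion (captured using weekday rounding observations". No fixed time window is given anywhere.

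The SAP section on additional analyses then uses attendance as an explanatory variable in two ways.

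- **Mediator with dose-response.** "We anticipate that the intervention effect on the following outcomes will be mediated by FCR attendance with a dose-response relationship". The list is "parent experience, family-centered care, parent activation, parent HRQOL, length of stay, and breastmilk feeding".
- **Joint predictors.** "we will fit regression models for each secondary outcome that simultaneously include measures of both virtual and in-person FCR attendance", in order to judge "whether the incremental benefits of higher FCR attendance are similar between both types of attendance". Length of stay is among the trial's outcomes for these models.

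The SAP's section on primary and secondary outcomes does recognise that longer stays bring more exposure. It deals with this by a log-denominator offset in the Poisson models for attendance and for errors. The mediation method for length of stay is not specified, and no landmark, fixed early window, time-varying attendance or time-to-discharge model is mentioned.

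**The concern.** When attendance is the outcome, dividing by the number of rounds is sensible. When attendance predicts length of stay, the predictor is known only once the outcome has occurred, and its denominator is that outcome in another form. An offset does not help, because attendance is now on the right-hand side of the model.

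If a family's chance of attending changes as the stay goes on, long and short stays average over different parts of that course. Average attendance then differs by length of stay even if attendance has no effect on discharge.

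At stake is the interpretation of the mechanism. The SAP says in advance that it expects this mediation. With falling attendance the artefact would look like support for it; with rising attendance it would look like evidence against it.

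**Working it through.** **1. The plan's own figure.** Inputs from the sample size text: 25% reduction in geometric mean stay, log SD 1.0, 2:1 allocation, 80% power, two-sided 5%, 4% attrition.

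- δ = −ln(0.75) = 0.2877
- n(control) = (1 + 1/2) × (1.960 + 0.842)² × 1.0² / 0.2877² ≈ 142.3, rounded up to 143
- Total = 3 × 143 = 429, and 429 / 0.96 = 446.9, so 447 randomized

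This reproduces the stated 447 and 429 (power with 143 + 286 is 80.2%).

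**2. Mechanism by hand.** Assume attendance starts at 40% and halves every 60 days. Average attendance over a stay of L days is 40% × (1 − e^(−kL)) / (kL), with k = ln 2 / 60 = 0.01155.

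| Log stay | L (days) | kL | Average attendance |
|---|---|---|---|
| 2.0 (mean − 1 SD) | 7.4 | 0.085 | 38.3% |
| 3.0 (mean) | 20.1 | 0.232 | 35.7% |
| 4.0 (mean + 1 SD) | 54.6 | 0.631 | 29.7% |

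Every family here behaves identically, yet longer stays show lower attendance.

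**3. Simulation A (multiplicative drift).** From the documents: 429 neonates, log stay 3.0 ± 1.0, weekday rounds. Assumed: control attendance starting at 30–40%, attendance ratio 1.5, between-family SD 0.5 on log attendance. Neither arm nor attendance affects stay. The method is product of coefficients on log stay. Ranges cover starting levels and repeated runs.

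| Drift in attendance | False indirect effect on stay | Trials significant |
|---|---|---|
| Halves every 30–60 days | 10–16% shorter | 96–100% |
| Halves every 120 days | 6–8% shorter | 50–73% |
| Halves every 240 days | about 4% shorter | 23–26% |
| Halves every 365 days | about 3% shorter | 14–20% |
| None | about 0 | – |
| Doubles every 60–120 days | 9–17% longer | – |

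**4. Simulation B (logistic drift), as a check on model choice.** 1,000 trials per setting, 286 + 143 neonates, no true effect. Assumed: baseline logit −0.4, arm effect +0.8, between-family SD 1.0. The indirect ratio is exp(a × b), with a the arm effect on attendance and b the slope of log stay on attendance given arm. At a weekly odds ratio of 0.85, a × b = 0.157 × (−0.921) = −0.145, and exp(−0.145) = 0.865.

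| Weekly odds ratio | Indirect ratio | Indirect effect significant |
|---|---|---|
| 0.85 | 0.865 | 99% |
| 0.90 | 0.903 | 81% |
| 0.95 | 0.945 | 33% |
| 0.98 | 0.974 | 9% |
| 1.00 | 1.000 | 5% |
| 1.02 | 1.023 | 8% |
| 1.05 | 1.056 | 30% |
| 1.10 | 1.100 | 77% |

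The false indirect effect is offset by a false direct effect of opposite sign (+0.149 on the log scale at 0.85). The test of arm on length of stay therefore rejects in only 4–6% of trials throughout.

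**5. The alternative.** With attendance restricted to the first 7 days and remaining stay as outcome among those still inpatient, simulation A gives an indirect effect of about 0, significant in 1–6% of trials. Simulation B gives slopes of −0.004 to 0.011 and a significant indirect effect in 3–4%, for weekly odds ratios 0.85 to 1.05.

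**6. Neonates lost to a landmark.** P(stay ≤ 7 days) = Φ(ln 7 − 3.0) = Φ(−1.054) = 14.6%, counted from admission. Simulation B rounded stays to whole days and kept those of 7 or more, leaving about 373 of 429.

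**The case against.** **The size rests on assumption.** The documents give no drift rate, direction or attendance level. A 10–16% effect needs strong falling drift and is not the expected size. Slow drift gives little bias, and rising attendance reverses the sign. All of this stands, which is why the result is given as a range.

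**The mediation method is not specified.** A whole-stay proportion in a product-of-coefficients model is the natural reading, not a stated one. A time-aware method is not excluded, but none is written, and the only attendance measure defined is the whole-stay proportion.

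**Mediation may be tested only after a positive effect.** The SAP states such a condition for quality of life. Applied to length of stay, a trial with no true effect would reach a significant favourable mediation result in only about 2–4% of cases with halving every 30–60 days. But the condition is not written for length of stay, and the virtual/in-person models carry none. Nor does it protect a trial with a real effect: with a true 25% reduction acting wholly outside attendance and halving every 60 days, the whole-stay mediator still credited attendance with a 10% reduction, significant in 91% of trials (landmark: about 0, 4%).

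**The analyses are exploratory.** A reader might infer that because length of stay sized the trial, its main result is at risk. The documents do not support that: the randomized comparison does not use attendance as a predictor.

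**Self-selection.** Virtual attendance is open only to subscribed intervention families, and both types of attendance are the family's choice. This is secondary and partly covered: the general model already has an arm term and transportation security. Residence-to-NICU distance is listed only as an effect modifier.

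**Conclusion.** The point holds for one outcome in one set of analyses. Used as planned on the natural reading, whole-stay attendance gives a biased slope and a biased indirect effect on length of stay whenever attendance drifts over the stay. The existence of the bias and its dependence on the direction of drift follow from the definition of the measure. Its size does not: it runs from negligible under very slow drift, through about 4% at a 240-day half-life, to 10–16% at 30–60 days, with the opposite sign if attendance rises.

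These sizes rest on the assumed attendance levels and drift, a log-normal stay with the protocol's mean and SD, and a product-of-coefficients analysis. The documents do not show that an artefact will necessarily confirm the anticipated mechanism. The primary outcome, the sample size and the randomized comparison of length of stay stand as they are. The plan should be corrected here because the better analysis uses data already being collected.

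**What to change.** For length of stay only, state in the SAP that whole-stay attendance will not be used as mediator or predictor. Choose one of the following in advance.

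- **Time-varying attendance.** Model weekday attendance to date as a time-varying predictor of subsequent discharge. This keeps all neonates.
- **Landmark.** Use attendance on weekday rounds in the first 7 days from enrolment/assignment, with remaining stay as outcome among neonates still inpatient at that point. The time origin must be stated: the participant log holds admission and enrolment dates separately, and virtual rounds are available only after invitation and subscription.

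Apply the same rule to the virtual/in-person models for length of stay. Keep the arm term there, or fit them within the intervention arm. Add residence-to-NICU distance to the listed covariates, and report the results as associations.

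**Cost.** SAP wording and a re-derivation from the weekday observations. The landmark drops about 15% of neonates from this exploratory analysis, conditions on still being inpatient after randomization (harmless only if assignment does not affect early discharge), and addresses early rather than whole-stay attendance. Neither option removes confounding by the family's own choice to attend.

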#### **Methods in analysis to handle protocol non-adherence and any statistical methods to handle missing data**

The primary analysis strategy – a modified intention-to-treat analysis – differs from intention-to-treat only in that it will not require replacing missing data with imputed values. This ‘complete-case’ analysis strategy assumes that missingness is at random. Sensitivity analysis using multiple imputation will be performed to assess the potential impacts of nonignorable missingness and alternative approaches for handling infants whose disposition is not to the home

and thus for whom the outcome may not be as applicable. In particular, for the few infants who transfer to another unit or hospital, the parent-reported outcomes and the 30-day revisit/readmission outcomes are of limited applicability. Our modified intention-to-treat analysis will include these subjects, but alternative analysis that excludes such outcomes from infants not discharged to home would be warranted. We will also estimate alternative treatment effects, such as per-protocol and as-treated.

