thus this outcome will be considered exploratory. Outcome distributional assumptions were based on data from our pilot trial or other relevant literature. Pilot trial baseline mean log transformed length of stay +/- standard deviation (SD) was 3.0 +/- 1.0 days. Minimally clinically important differences (MCID) were based on the literature when available or via consensus opinion elicited from NICU clinicians we consulted. For the length of stay outcome, experts specified that a 25% reduction in geometric mean length of stay was of interest. A randomized sample of 447 neonates (298 intervention, 149 control) subject to 4% attrition in each arm yields a sufficient sample size (429 neonates) to provide 80% power (under two-sided testing, alpha=5%) to detect this MCID. This estimated attrition is based on 4 of 110 randomized subjects in the pilot trial being excluded from final analysis (e.g., child protective visitation restrictions placed after randomization). Parent-reported outcomes assume a survey response rate of 75% (thus n=321 parents). Note: Regarding sample size for the interviews, we anticipate interviewing ~15 parents, ~10 nurses, and ~10 physicians. Consistent with standard qualitative methods, we will continue to sample interview participants until we reach thematic saturation, thus we cannot specify a priori the exact number of interviewees.

All virtual FCR encounters will occur using an application platform that is approved by Information Technology at UC Davis Health System as meeting HIPAA and HITECH data security requirements. The only telehealth communication that will occur will be through the HIPAA-compliant application. No telehealth encounter will be recorded or stored in any way.

Participants will decide to what extent they want to participate in the interviews and surveys. There will be no personal or intrusive questions. In all steps of this pilot study, the risk of loss of confidentiality is very low given the measures described above to protect PHI.

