## STATISTICAL ANALYSIS PLAN

### Statistical methods for primary and secondary outcomes

Our primary analysis strategy will analyze all available data from participating family units and their members, with groups defined according to the randomized assignment (intervention versus control) for that family unit. We will use graphical and analytical descriptive statistics to summarize infant, parent, and family unit characteristics. We will use methods for clustered survey data to adjust confidence intervals for family units with multiple parental respondents. We will not use cluster-adjusted confidence intervals for family units with multiple infants unless the mean number of infants per family unit unexpectedly exceeds 1.10.

We will use generalized linear models to estimate intervention effect sizes and confidence intervals and to test hypotheses for outcomes. Independent variables will include a binary indicator for intervention assignment along with a parsimonious set of subject characteristics as covariates (parent age, race, ethnicity, gender, education, transportation security, marital status, other children dependents, digital literacy score). We will specify the generalized linear mixed models as linear, logistic, or Poisson regressions, according to the outcome type. Random effects will be specified to accommodate the multilevel structure of the data and the nesting of longitudinal measurements, when applicable, within parents and the nesting of parents and infants within family units.

To account for increased exposure among subjects with longer neonatal intensive care unit (NICU) stays when analyzing the primary outcome, we will use Poisson regression to compare rates for the family-centered rounds (FCR) parent attendance outcome between intervention vs. control group subjects, using the numerator for this outcome as the dependent variable and using the logarithm of the denominator as an offset term. We will also use Poisson

regression for analyzing the error rate outcomes, with the offset being the logarithm of the number of days in the NICU. The exponentiation of the Poisson regression coefficient for the treatment indicator will thus represent an adjusted between-arm rate ratio for FCR parent attendance.

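### The main analysis of 90-day breast milk feeding is complete-case and leaves out the discharge feeding status that the EHR should hold for every infant

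*Combined protocol and SAP*

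**What the plan says.** Protocol section 2 (Aim 2): "We will compare breast milk feeding at discharge and 90 days from discharge". Section 7 (Data collection) gives the sources: "breast milk feeding at discharge (captured using EHR data) and at 90 days after discharge", the later value coming from the parent survey. Section 8 adds that outcomes resting on the EHR cover all subjects.

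Section 8 (Sample size): "Parent-reported outcomes assume a survey response rate of 75% (thus n=321 parents").

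The SAP section on non-adherence and missing data describes a modified intention-to-treat analysis in which "it will not require replacing missing data with imputed values". It says that this complete-case "analysis strategy assumes that missingness is at random", and then: "Sensitivity analysis using multiple imputation will be performed to assess the potential impacts of nonignorable missingness". Neither this section nor protocol section 8 names the variables in the imputation model.

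The SAP section on primary and secondary outcomes lists the model covariates: "parent age, race, ethnicity, gender, education, transportation security, marital status, other children dependents, digital literacy score". Discharge feeding is not among them. The same section allows random effects for repeated measurements where applicable, but the time-by-arm model is spelled out only for health-related quality of life. Breast milk feeding falls under the remaining outcomes.

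**The concern.** Discharge feeding is the earlier value of the same outcome and probably its strongest predictor. It should be known for infants whose parents do not reply. A complete-case model with arm and nine parent characteristics makes no use of it.

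This affects validity as well as efficiency. Data can be missing at random given everything observed, including discharge feeding, while the complete-case model is still biased because it does not condition on discharge feeding. The plan's stated assumption is therefore not enough to justify its stated method for this outcome. At stake is the 90-day part of hypothesis 2(a): some precision, and possibly the size or even the presence of an arm difference.

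**Working it through.** **1. The plan's own figures.** With SD 1.0 on the log scale, a 25% reduction (ln 0.75 = -0.288), two-sided alpha 5%, 80% power and 2:1 allocation, the requirement is 143 + 286 = 429 (power 80.2%). Allowing for 4% attrition, 429/0.96 = 447. Survey respondents: 0.75 × 429 = 321.75, stated as 321. All reproduce. Infants without a 90-day value: 429 - 321 = 108, or 25%. This assumes one reply per infant and that the 75% applies at 90 days.

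**2. Formulas.** The documents give no feeding rates, so every rate below is an assumption. In each arm let p be the proportion fed breast milk at discharge, q1 and q0 the 90-day rates in those fed and not fed at discharge, and r1 and r0 their response rates.

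- True 90-day rate: T = p·q1 + (1-p)·q0
- Complete-case rate: C = [p·r1·q1 + (1-p)·r0·q0] / R, where R = p·r1 + (1-p)·r0
- Complete-case variance: C(1-C)/(nR)
- Using discharge status within arm (the large-sample equivalent of imputing by arm and discharge feeding): expectation T; variance [p(1-p)(q1-q0)² + p·q1(1-q1)/r1 + (1-p)·q0(1-q0)/r0]/n

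The calculations are unadjusted.

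**3. Response unrelated to feeding.** Take p = 0.60 control and 0.75 intervention, q1 = 0.60, q0 = 0.02, r1 = r0 = 0.75.

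- Complete-case: 0.368×0.632/107.25 + 0.455×0.545/214.5 = 0.00332, SE 0.0577
- Using discharge status: 0.2832/143 + 0.3096/286 = 0.00306, SE 0.0553

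There is no bias, and the complete-case SE is 4% larger. With control discharge feeding at 50% or 70%, it is 5% or 3% larger.

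**4. Response depends on discharge feeding, equally in both arms, with a true effect.** Same q1 and q0, intervention 15 points higher at discharge, 75% response overall. The true difference is 0.15 × 0.58 = 0.087. Shrinkage of the complete-case difference:

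| Response gap | Control 50% | Control 60% | Control 70% |
|---|---|---|---|
| 10 points | 2% | 5% | 8% |
| 20 points | 6% | 11% | 16% |
| 30 points | 10% | 18% | 25% |

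Using discharge status recovers 0.087. It cuts the SE by about 7-12% at a 30-point gap.

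A second set of assumed rates (p = 0.60 and 0.70, q1 = 0.65, q0 = 0.05, response 81% and 65%):

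- Control: C = (0.3159 + 0.0130)/0.746 = 0.441
- Intervention: C = (0.3686 + 0.0098)/0.762 = 0.496
- Difference 0.056, against a true 0.47 - 0.41 = 0.060

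**5. Same pattern in both arms, no effect.** With p = 0.60 in both arms and response 85% and 60%, both complete-case rates are 0.458 instead of 0.410. The difference is 0, so the arm comparison is unbiased.

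**6. Pattern differs by arm, no effect.** One arm has response 85% and 60%, so C = (0.3315 + 0.0120)/0.75 = 0.458. The other has 75% and 75%, so C = 0.410. The spurious difference is 0.048 in either direction, and simulation (10,000 trials, 143 vs 286) gives about 13% two-sided rejection. With a true difference of 0.060 the complete-case result is 0.012 or 0.101. Using discharge status removes the bias in each case.

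**7. Response depends on 90-day feeding itself (not missing at random).**

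- Equally in both arms: the odds among responders are the true odds times the same ratio of response rates, which cancels. With the rates of step 3 and a 20-point response gap, the true, complete-case and discharge-based odds ratios are 1.434, 1.434 and 1.470. The risk differences are 0.087, 0.090 and 0.095.
- Differently by arm, no effect (p = 0.60, q1 = 0.65, q0 = 0.05; response 88% and 65% in one arm, 75% throughout in the other): complete-case 0.3608/0.7443 - 0.41 = 0.075; using discharge status 0.456 - 0.41 = 0.046. The bias shrinks but remains.

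**The case against.** A reader might infer that the complete-case result is biased whenever response is related to feeding, or that the arm difference is understated if families still giving breast milk reply more often. The documents do not support either reading. They give no feeding rates and no response mechanism, and steps 5 and 7 show cases where the arm comparison or the odds ratio is untouched. In the equal-in-both-arms case of step 7, imputing from discharge feeding slightly overstates the effect. There is also no bias if arm and the listed covariates fully explain the link between response and feeding. So no method is best under every mechanism. What remains is that step 7 lies outside missing at random, the assumption on which the plan itself relies.

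A reader might also infer that every non-responding family is lost and that missing data are ignored. Section 7 invites each eligible parent separately and adds a contact for later-discharged siblings, so an infant is lost only when none of these succeeds. Multiple imputation is planned, and nothing excludes discharge feeding from it. But nothing includes it either, and if the two analyses disagree the headline stays complete-case.

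Other fair points: section 8 concedes that survey results generalise only to populations like the respondents; the sample-size text already allows for 75% response; and the persistence rates used above are undocumented. In the 60% example at a 20-point gap, the bias is about 0.009 against an SE of about 0.059, roughly 0.16 SE. These points limit the importance of the matter. They do not explain why a variable already collected should go unused.

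**Conclusion.** The concern holds in a limited form. The main analysis of 90-day breast milk feeding, a secondary outcome, omits about a quarter of infants and does not use the discharge feeding status planned from the EHR.

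Under missing at random and the assumed rates, the cost runs from modest to material. Precision loss is small when response is unrelated to feeding. Attenuation appears when response follows discharge feeding equally in both arms and there is a true effect. A spurious difference of about 5 points arises in the assumed example where that dependence differs by arm. The last case is the most serious. It is plausible, though not shown, because parents know their assignment and the intervention aims to change their engagement.

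The direction and size of any bias rest on assumed feeding and response rates, a binary outcome and unadjusted calculations. The trial's primary outcome, parent attendance at rounds, is not affected.

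**What to change.** For 90-day breast milk feeding only, prespecify a main analysis that uses discharge feeding, in one of two ways:

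- Run the already planned multiple imputation separately by arm. Use EHR discharge feeding, feeding initiation and the model covariates as predictors, then fit the planned model to all eligible neonates. Impute any covariate that is itself missing: the documents do not say where digital literacy or transportation security is recorded, and if it is the survey, non-responders lack those values too.
- Or fit a joint or mixed model of discharge and 90-day feeding with arm, time and their interaction, using the random effects that the SAP already allows.

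Do not add discharge feeding as a covariate in the outcome model. It is measured after randomisation and is itself an outcome, so adjusting for it could remove part of the effect. Report complete-case alongside, and add an analysis in which response departs from missing at random, including departures that differ by arm.

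The cost is SAP wording and some programming; no new data or family contact is needed. The downside is that the headline for one secondary outcome depends on an imputation or joint model. The minimum change is to name discharge feeding as a predictor in the planned sensitivity imputation.
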